Strategies to reduce the social gradient in uptake of bowel cancer screening: the ASCEND Study

Bowel cancer is the third most common cancer in the UK, and the second most common cause of cancer death. This significant public health burden can be diminished by screening using the guaiac faecal occult blood test (gFOBt), which randomised controlled trials (RCTs) have demonstrated can reduce bowel cancer mortality (1). The National Health Service (NHS) Bowel Cancer Screening Programme (BCSP) commenced biennial screening in 2006 and now offers gFOBt to 60-74-year-olds in England.

There is a strong socio-economic status (SES) gradient in uptake of gFOBt screening in the BCSP which will ultimately create inequalities in bowel cancer outcomes. Previous research to tackle socio-economic inequalities in uptake has focused on specific under-served groups, rather than reducing the gradient in uptake across the entire population.

The ASCEND Study was funded by an NIHR Programme Grant for Applied Research that culminated in four national, cluster-randomised trials, embedded in the English Bowel Cancer Screening Programme. The trials compared 'usual care' with usual care plus different supplementary materials designed to reduce the SES gradient through more effective communication of the screening offer. Interventions were selected on the basis of prior evidence of their efficacy to improve understanding or screening uptake among low SES groups.

Four interventions were tested: i) a supplementary 'Gist' leaflet summarising key information in simple language ii) a supplementary 'Narrative' leaflet describing people's stories , iii) General Practitioner (GP) endorsement on the invitation letter and iv) an Enhanced Reminder letter that reiterated the screening offer. The SES marker was the Index of Multiple Deprivation (IMD) score for each home address. The primary endpoint was the gradient in uptake across IMD quintiles.

The Gist and Narrative trials showed no effect on the SES gradient in uptake or overall uptake (p ≥ 0.1). The GP endorsement trial showed no effect on the SES gradient, but increased overall uptake (adjusted Odds Ratio (adj OR) =1.07, 95% CI 1.04-1.10, p<0.0001). The Enhanced Reminder trial showed a significantly increased uptake with decreasing SES (p=0.005), as well as higher overall uptake (adj OR=1.07, 95% CI 1.03-1.11, p=0.001). Therefore, of the plausible interventions, only the Enhanced Reminder reduced the SES gradient, but both the GP endorsement of the screening offer and the Enhanced Reminder had an effect in increasing uptake.

In the ASCEND trials, the supplementary leaflets and GP endorsement were added to the prescreening invitation letter, designated S1 in the Bowel Cancer Screening System (BCSS), which is sent out a week before the FOBt kit. ASCEND2 has been designed as follow-on to assess the effectiveness of a GP endorsement (GPE) banner on the S9 kit invitation letter which is sent with the FOBt kit. The underlying rationale in undertaking this additional trial is that the recipient of the test may be more susceptible to a GP endorsement in the letter sent at the same time as the FOBt rather than a week earlier as in the ASCEND trial (intervention 3). There is no current literature published on the English BCSP that makes a distinction between the role of the S1 and S9 invitation letters. Intervention 3 had to be incorporated into the S1 pre-invitation letters due to space constraints in adding additional text to the S9 kit invitation letter. The space issue has since been resolved and now there are no barriers to assessing the effect of moving the GPE banner to S9 letter. This will require a minimal amount of cost and effort to implement as the necessary changes have already been programmed into the BCSS.

We surmise that receiving an endorsement from the GP when you receive a kit is likely to be more effective than the modest increase in uptake that was seen with the Enhanced Reminder intervention. If we can achieve a 3% increase in uptake this would lead to 35,000 more people being screened every year and result in improvements in survival and reduced inequalities.

Aims and Objectives

The aim of this study is to increase uptake in the BCSP and to reduce SE inequalities in bowel cancer screening uptake but not compromise uptake in any of the SE groups.

[figure not shown]
Our principal objective is therefore to: examine the effectiveness, cost and cost effectiveness of an individual intervention at the invitation stage that can reduce the SE gradient in uptake and can be easily built into the current BCSP delivery system.

The control (comparison) group for this RCT is usual practice.

Study Design

ASCEND2 is a follow-on study to the ASCEND research programme and designed as a randomised controlled trial (RCT) using a general practice endorsement (GPE) on the BCSP kit invitation letters. As part of the ASCEND programme four different strategies (interventions) were developed and then tested in independent RCTs. Interventions 3 and 4 involved modifications to current letters produced by the Bowel Cancer Screening System: the invitation for screening (the S1 letter) and the reminder letter (S10). The invitation process is described in Figure 1 below.

[figure not shown]
Figure 1:

The study design of ASCEND 2 (intervention 5) is identical to that of intervention 3 except that the intervention is now included at the S9 stage. The S9 kit invitation letter is sent out to screening eligible individuals one week after they have been sent their initial S1 pre-invitation letter. The kit invitation includes the FOBt kit with instructions along with a cover letter explaining what has been sent and how to return the completed kit.

General practices will have been recruited as part of the ASCEND study prior to intervention 3 and those that have consented will be included in intervention 5. Consenting practices have agreed to include their names on BCSP letters to eligible individuals for the duration of the programme and they will be informed of the plan to undertake an additional intervention via the final study results letter. Screening eligible individuals, who are registered with practices that either did not respond to our request or actively expressed their disapproval, will not be randomised to receive this intervention (see Figure 2).

[figure not shown]

We have worked extensively with the Health & Social Care Information Centre (HSCIC), the organisation responsible for the design and maintenance of the Bowel Cancer Screening System (BCSS). The system is responsible for identifying the population eligible for screening in each of the five hubs and creating all the letters that are sent to the screening subjects and their GPs. For the purpose of our study the HSCIC modified the BCSS to enable selection of invitees registered with GP practices that endorse the BCSP prior to creation of each kit invitation letter (S9). In addition, the BCSS will be enabled to take into account the dates when GP-endorsed invitations need to be produced in any of the five hubs. The processes involved within the BCSS and the hubs are shown below in Figure 3.

The duration of this trial is 30 working days in each hub which will result in 15 clusters of invitees randomised to receiving an endorsed kit invitation letter and 15 control clusters in each hub. We plan that this intervention will take place in all hubs between Monday 1st Feb and Friday 11th March 2016.

Figure 3:

Comparators

Intervention 5 will provide data to compare the effectiveness of a GPE banner included on the S9 kit invitation letter against the usual S9 letter in the BCSP: it shall not involve any structural changes to the S9 letter.

Randomisation

Cluster randomisation will be used in this trial. Individuals who are routinely invited for screening in the NHS BCSP in England will be allocated to receive an intervention on randomly selected days within a pre-specified time-period. In consultation with all BCSP hubs we will identify trial dates which will enable us to run our intervention outside major public holidays or significant updates to the Bowel Cancer Screening System (BCSS). Prior to the start of the trial each of the BCSP hubs will receive a table with dates on which their population is due to receive GPE kit invitation letters (the intervention). These tables with randomisation dates will also be given to Health & Social (HSCIC), the organisation responsible for the BCSS.

Eligible population

Men and women aged between 60-74 years who live in England and are registered with a GP are eligible to be screened for bowel cancer in England and are therefore eligible to be included the trial. Invited subjects may contact their BCSP hub and opt-out of the current screening episode and others for reasons of choice or poor health can be ceased from the screening programme. 'Ceased' subjects, if ceased prior to their screening due date will not be invited to be screened.

Because the screening programme started in 2006 many members of the eligible population will have been invited and/or participated in previous rounds of screening.

Consent

Consent forms are not applicable in this study as the interventions are taking place as part of the subject's usual involvement with the NHS Bowel Cancer Screening Programme.

The intention of this trial is to amend the S9 kit invitation letter currently sent out to eligible subjects and to identify whether a GPE banner will lead to a corresponding change in uptake of screening. The design of this intervention does not represent a change to the current remit of the NHS BCSP, and as it closely supports screening activities, does not significantly deviate from the originally approved purposes. The activities of the NHS BCSP are covered under an existing Confidentiality Advisory Group (CAG) Section 251 approval with regard to the handling of patient-identifiable data (Ref: PIAG 1-08(a)/2003) All data sent from the HSCIC to the BCSP Data Analyst will be pseudoanonymised ensuring no disclosure of identifiable information will be made to the team. Further information regarding the data management process is described on page 13.

Exclusion criteria

We will randomise eligible people to receive this intervention only if they are registered with practices that have agreed to endorse the BCSP (as shown in Figure 2). 80% of general practices consented to their name being used on BCSP invitation letters so the majority of eligible people will be included in the randomisation.

Outcomes

Primary Outcome

The primary outcome of this study is the proportion of people in each Index of Multiple Deprivation (IMD) quintile returning an adequate faecal occult blood test (FOBt) within 18 weeks of being sent their initial invitation (S1). An adequate FOBt in this study is defined as reaching a definitive FOBt outcome of either a 'Normal' (no further clinical investigation required) or 'Abnormal' (referral for colonoscopy).

We will use IMD quintile here because of its demonstrated ability to explain area-level variation in bowel cancer screening uptake (2). IMD is freely available and widely accepted and used, enabling direct comparison of our results with other studies. IMD will be applied using the geographic unit of Lower Super Output Area (LSOA) level.

We have chosen to assess the proportion of FOB tests returned at 18 weeks from the pre-invitation to coincide with when the Bowel Cancer Screening System (BCSS) closes an episode due to non-response.

Secondary outcomes

- i) Time taken to return FOBt by IMD quintile
- ii) Proportion of spoilt kits by IMD quintile
- iii) Proportion of non-delivered kits by IMD quintile
- iv) Incremental cost per screening invitation
- v) Incremental cost per screening invitation, both by IMD quintile and overall
- vi) All of the above outcomes analysed using other socioeconomic (SE) variables

Statistics

Sample size

To calculate the required study size, we need to take into account:

- 1. The size of the effect/interaction we wish to detect.
- 2. The anticipated distribution of socioeconomic status and the expected participation by socioeconomic status in the control arm and by screening round.
- 3. The proportion of GPs agreeing to be included in the trial.
- 4. A variance inflation factor to account for the cluster (hub-day) randomisation.
- 5. The size of the effect/interaction by screening round.

In ASCEND, the combined effect of GP endorsement with introductory letter was a 3% overall increase in participation. As a failsafe, we design the trial using the more conservative 2% overall

estimate. We posit an interaction such that in the least deprived quintile, there is a 1% increase in participation with the intervention, in the second least deprived a 1.5% increase, and so on, with a 3% increase in the most deprived quintile.

The control group from the GP endorsement trial in ASCEND had the socioeconomic status distribution and completion rates by socioeconomic status shown in Table 1. Note that the percentages per quintile are not all 20% since socioeconomic status is associated with age and place of residence (in the latter case therefore being influenced by the proportions of subjects by hub). We anticipate these rates in the control group of the proposed trial and anticipate the intervention participation rates in the final column of Table 1.

We calculated the required sample size using the method of Brentnall et al (2012). To obtain 90% power to detect the interaction as significant at 5% level with 2-sided testing, in an individually randomised study, we would require 11,714 individuals in each arm. In ASCEND, 80% of the GP's approached agreed to participate in the GP endorsement trial, giving 14,643(=11,714/0.8) subjects per trial arm. Also in ASCEND, we estimated a variance inflation factor for cluster randomisation of 1.7, but results post hoc suggest that a larger inflation would be more appropriate. We therefore use an inflation factor of 2.5, giving a total study size of 36,608 per arm, a total randomised of 73,216. Assuming approximately 3,000 kits are sent per hub-day, this indicates that we should randomise 25 hub-days. To cope with any plausible failures of our assumptions, we propose to randomise 100 hub-days to allow for subgroup analyses, completing trial accrual from the five hubs in four working weeks with a target population of 300,000.

In order to also consider subgroups by screening round, we propose a further increase to 150 hubdays. With 150 hub-days, we have a target population of 450,000. The smallest screening round subgroup in ASCEND1, prevalent screen first-time, comprised around 15% of the recruits. This would give 67,500 in this smallest subgroup. Within screening round subgroups, the variation between hub-days is around 20% lower than in the population as a whole, which in turn suggests a variance inflation factor of around 2. For 90% power for the same size of effect as expected overall, we would need 2 x 14,643 per arm, just under 30,000 per arm, 60,000 in total. Thus, the study size of 150 hubdays is likely to be more than adequate for subgroup comparisons. The trial will involve no additional costs or work on the part of hub staff if the trial size is increased as the GP endorsement and random allocation will be programmed within the Bowel Cancer Screening System.

Table 1. Expected socioeconomic status distribution, and intervention and			
control completion rates			
Socioeconomic	Percentage in	Control group	Anticipated
status (national	each quintile	completion	intervention
IMD quintile)	from ASCEND	percent by	group completion
		quintile from	percent
		ASCEND	
1 (least deprived)	23.5	66.0	67.0
2	23.5	62.6	64.1
3	21.1	58.0	60.0
4	17.3	51.5	54.0
5 (most deprived)	14.6	42.6	45.6

Data Analyses

We will undertake a descriptive analysis of socio-demographic characteristics in the two arms across each intervention and analyse uptake differences by logistic regression (LR). Although randomisation should ensure comparability, the analysis will be performed with and without adjustment for age, sex, screening round and hub (4). The question of whether the intervention has a greater impact on uptake in the lower SE groups will be assessed by a test of interaction between trial arm and IMD quintile in the LR analysis. We will also use hierarchical LR to account for heterogeneities (i.e. due to varying policies and procedures in PCTs). We will adjust for incident episode versus prevalent episode status and check for heterogeneity of effects between incident and prevalent screens. The use of the maximum sample size from the calculation above will also enable subgroup analyses by sex, age, hub and incident versus prevalent screening round.

A secondary analysis of time taken to return the FOBt by IMD quintile will be examined using the log rank method (5). When comparing the intervention against usual practice, we will in the first instance compare all interventions to all controls on an intention-to-treat basis.

Finally, we will also examine effectiveness in terms of the SE variables identified in the ASCEND study.

Data Management

A Data Analyst working on behalf of all BCSP hubs has designed and piloted the data extraction algorithms. The raw data will be extracted by Health & Social Care Information Centre (HSCIC) from BCSS and pseudo-anonymised then given to the Data Analyst to clean. The postcode variable will be substituted with Index of Multiple Deprivation (IMD) score by HSCIC.

The Data Analyst has specified the data to be extracted by HSCIC and the National Office on behalf of the ASCEND2 research team. No patient identifiable information is required. Data transfer between HSCIC/the National Office and the Data Analyst will be via encrypted network connection (NHS.NET) and/or NHS Secure File Transfer (SFT).

The pseudo-anonymised raw data will be processed and further anonymised into the format required by the ASCEND2 academic statisticians. Any permutations of geo-demographic variables that could lead to potentially identifiable patient information will be subject to further levels of anonymisation.

Although anonymised, data transfer between the Data Analyst and the ASCEND2 research team will use password protected files and SFTP. The ASCEND research team will undertake to keep the data secure, and not to attempt to reverse engineer, link the data to other datasets or use the data for any purpose other than the ASCEND2 project. The project will adhere to the NHS Cancer Screening Programmes Confidentiality and Disclosure Policy.

The data will be extracted from the BCSS 18 weeks following the last intervention date.

Quality Control and Quality Assurance

Evaluation of Intervention Fidelity

This intervention requires insertion of the name of the subject's general practice into the S9 kit invitation letter. This can only be achieved by implementing changes on the BCSS. As part of the previous ASCEND trial we conducted extensive consultations with HSCIC whose programmers applied the necessary changes to the BCSS to ensure that general practice-endorsed kit invitation letters can be generated on pre-specified random dates. Changes to the BCSS include addition of a variable that will indicate whether a subject received an intervention or whether he/she was a part of the control cluster.

The Trial office will provide HSCIC with details of all the general practices that agreed to endorse the BCSP and randomisation dates for each hub.

The process diagrams for the GPE letters are detailed in Figure 3.

Monitoring and Auditing

The Imperial College Joint Research Compliance Office, on behalf of Imperial College as Sponsor, will monitor and conduct random audits on a selection of studies in its clinical research portfolio. Monitoring and auditing will be conducted in accordance with the Department of Health Research Governance Framework for Health & Social Care (April, 2005), and in accordance with the Sponsor's monitoring and audit policies and procedures.

Ethics

Ethical Approval

Ethical Approval will be obtained from the UK National Research Ethics Service, prior to commencement of this study and Local Ethics Committee approval has also been sought and obtained from the Bowel Cancer Screening Programme Research Committee.

Ethical Approval for the NIHR-funded ASCEND study was obtained from UK National Research Ethics Service, London – Harrow Ethics Committee, Reference number 12/LO/1396 prior to commencement of this study.

Risks for Trial Subjects

Risks to the subjects associated with this study are not any higher than the risks associated with usual contact with the BCSP. The ASCEND project was designed with advice from patient representatives and charities who found no cause for concern.

ASCEND2 is a follow-on trial that is identical in design to Intervention 3 from the ASCEND study, with the GPE banner simply added to a different invitation letter (the test kit or S9 letter rather than the pre-invitation or S1 letter) that is currently in use in the BCSP.

Clinical Trial Documentation

In accordance with Imperial College Retention Schedule, the Imperial College London Joint Research Compliance Office and the EU Good Clinical Practice Directive 2005/28/EC, all primary research data will be retained for a minimum period of 10 years following completion of the study.

Publication Policy

All publications and presentations relating to the study will be discussed and authorised by the Chief Co-investigators. Project Co-investigators will be listed and will have a chance to comment on draft papers for publication. Contributors will be cited by name if published in a journal where this does not conflict with the journal's policy. Authorship of parallel studies which are not initiated by the Chief Co-investigators will be according to the individuals involved in the project but must acknowledge the contribution of the project investigators and collaborating institutions: NHS Bowel Cancer Screening Programme, University College London, Imperial College London and Queen Mary University of London.

References

2. [name] C, Baio G, Raine R, Snowball J, Morris S, Atkin W, et al. Inequalities in participation in an organized national colorectal cancer screening programme: results from the first 2.6 million invitations in England. Int J Epidemiol. 2011;40(3):712-8. Epub 2011/02/19.

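### The random draw of hub-days is stated without balancing by weekday or week; six full weeks allow an exact 3:3 weekday split per hub, for a small and nearly free gain in precision

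*Protocol*

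**What the plan says.** The Randomisation section says that invitees are "allocated to receive an intervention on randomly selected days within a pre-specified time-period". Trial dates are to avoid major public holidays and significant system updates, and each hub receives its table of intervention dates before the start.

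Study Design gives the numbers: "The duration of this trial is 30 working days in each hub", resulting in "15 clusters of invitees randomised to receiving an endorsed kit invitation letter and 15 control clusters in each hub". The trial is planned for all hubs "between Monday 1st Feb and Friday 11th March 2016".

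Sample size takes the hub-day as the cluster. ASCEND's variance inflation factor was 1.7, but "results post hoc suggest that a larger inflation would be more appropriate", and 2.5 is used. The final plan is 150 hub-days at about 3,000 kits each.

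Data Analyses lists age, sex, screening round and hub as adjustment variables. It adds hierarchical logistic regression for differences in local policy, tests the arm-by-IMD interaction, and plans subgroup analyses that include hub. Time to kit return is compared by log-rank. Neither the description of the draw nor the adjustment set mentions weekday or calendar week.

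**The concern.** When days are the randomised units, weekday and calendar week are the features of a day known in advance. The protocol reports that hub-days varied more than had been estimated. Its stated response is a larger inflation factor and more hub-days, with no stated restriction on which days are drawn.

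If part of that variation follows weekday or week, a free draw leaves it in the arm comparison, where a restricted draw would remove it at almost no cost. What is at stake is precision. Days are still allocated at random, so the comparison stays unbiased.

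**Working it through.** **The plan's own chain.** 11,714 / 0.8 = 14,643 per arm; x 2.5 = 36,608 per arm; x 2 = 73,216; / 3,000 = 24.4, rounded up to 25 hub-days. 150 x 3,000 = 450,000, or 225,000 per arm. These steps reproduce. The starting figure of 11,714 does not come back from a direct trend calculation on Table 1, and the cited method is not in the documents. That is a separate matter, and the standard errors below do not use it.

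**Feasibility.** Monday 1 February to Friday 11 March 2016 holds 30 working days: six of each weekday, in six weeks of five days. A 3:3 split per weekday is exact. A week of five days cannot be halved; the best split is 2:3 or 3:2. The two restrictions fit together: three weeks with 3 intervention days and three with 2 give 3 x 3 + 3 x 2 = 15.

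**Imbalance under an unrestricted 15:15 draw in one hub.**
- All five weekdays 3:3: C(6,3)^5 / C(30,15) = 3,200,000 / 155,117,520 = 0.021.
- One given weekday (hypergeometric, 6 of 30 with 15 drawn): 3:3 with probability 0.35, 4:2 or 2:4 with 0.48, 5:1 or worse with 0.17.
- At least one weekday 5:1 or worse: 0.55 (100,000 simulated draws).
- At least one week 4:1 or worse: 0.87 (same simulation).

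Pooled over five independent hubs, the intervention count for a weekday has mean 15 of 30. Its variance is 5 x 6 x 0.5 x 0.5 x 24/29 = 6.2, so its SD is 2.5.

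**Size of the day-to-day variation.** From Table 1, weighted control uptake is 57.6% and weighted intervention uptake 59.5%, a planned overall effect of 1.88 points.
- Intracluster correlation: (2.5 - 1) / (3,000 - 1) = 0.00050.
- Between-day SD: sqrt(0.00050 x 0.576 x 0.424) = 0.011, or 1.1 points.
- Contribution of all between-day variation to the 75 v 75 contrast: 1.1 x sqrt(2/75) = 0.18 points.
- Total pooled SE: sqrt(2.5 x (0.576 x 0.424 + 0.595 x 0.405) / 225,000) = 0.0023, or 0.23 points. With 180,000 per arm (80% participation) it is 0.26.
- Within one hub, 15 v 15 days and 45,000 per arm: 0.52 points, or about 0.6 at 80% participation.

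**Possible gain.** Let f be the share of between-day variance that balancing and the matching model terms remove. The documents do not give it, so the values are assumptions. Factor = 1 + 1.5 x (1 - f); SE ratio = sqrt(factor / 2.5).

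| Assumed f | Factor | SE reduction | Pooled SE (points) | One-hub SE (points) |
|---|---|---|---|---|
| 0% | 2.50 | 0% | 0.232 | 0.52 |
| 10% | 2.35 | 3% | 0.225 | 0.50 |
| 25% | 2.125 | 8% | 0.214 | 0.48 |
| 50% | 1.75 | 16% | 0.194 | 0.43 |

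**The case against.** **Silence is not proof of an unrestricted draw.** The protocol does not say how the date tables are produced, and a weekday-restricted draw would fit every sentence in it. This stands, so the point is that no balancing is stated. Further model terms may also be left to an analysis plan. The draw itself, however, is settled once the dates are issued.

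**The variance is already allowed for.** The factor of 2.5 covers total hub-day variation whatever its source, and the size was raised from about 25 hub-days to 150. This also stands. On the figures above the planned overall effect is 7 to 8 standard errors (1.88 / 0.26 and 1.88 / 0.23), so the pooled uptake comparison does not need the gain.

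**A reader might infer that weekday imbalance could pass for the effect or hide it.** The documents do not support that. The 1.1 points is the SD of a single day. In the pooled contrast all between-day variation amounts to 0.18 points. If a quarter or a half of it were due to weekday or week, the contribution would be 0.09 or 0.13 points. The 55% figure also describes the worst weekday in one hub, and imbalances partly offset across five hubs.

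**A reader might also infer a clear gain for the primary test**, because the protocol applies the factor of 2.5 to the interaction sample size. A day effect shared by all quintiles largely cancels in the arm-by-IMD interaction. Only a weekday or week effect that differs by deprivation would remain, and nothing in the protocol points to one.

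**No part of the variation is attributed to weekday or week.** Correct; the gain may be nil.

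**Conclusion.** The point holds as a minor improvement to the design. The protocol states a 15:15 draw within hub, with no balancing by weekday or week and no adjustment for them, when exact weekday balance is available. The consequence is at most some lost precision.

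The reduction in the standard error of the overall effect runs from nil to 16% as the assumed weekday or week share of hub-day variance runs from 0% to 50%. The range also rests on the protocol's factor of 2.5 and 3,000 kits per hub-day.

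The gain would be most useful in the by-hub subgroups, where 15 v 15 days give a standard error of about 0.5 to 0.6 points. It may also help time to kit return, since the weekday of dispatch decides where weekends fall in the return interval; that last step is reasoning and is not taken from the protocol. Neither the pooled conclusion on uptake nor, to any large extent, the interaction test depends on this point.

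**What to change.** Before the date tables go to the hubs and HSCIC, restrict the draw within each hub to 3 intervention and 3 control days for each weekday, with 2 or 3 intervention days in each calendar week. Choose at random among the date lists that meet both conditions, and state the restriction in the Randomisation section. If the draw is already restricted, stating so settles the first part.

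Add weekday and week to the adjusted model, so that the estimated standard error reflects the balance. If the dates have already been issued, these terms alone would recover most of whatever gain exists.

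The cost is a different date list and a few model terms. There is no operational cost, because the dates are tabulated in advance and programmed into the screening system. No one recruits participants who could exploit a more predictable pattern. The downside is a few degrees of freedom: weekday and week as terms common to all hubs use 4 + 5 = 9, which takes 150 - 5 - 1 = 144 down to 135. Separate weekday terms in each hub, without week, would leave 150 - 25 - 1 = 124.

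### The 11,714 per arm said to give 90% power for the arm-by-IMD interaction is about nine to eleven times too small on the protocol's own Table 1

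*Protocol*

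**What the plan says.** The Sample size section posits a rising benefit with deprivation: "in the least deprived quintile, there is a 1% increase in participation with the intervention, in the second least deprived a 1.5% increase". The benefit keeps rising by half a point per quintile and reaches 3 points in quintile 5. Table 1 gives each quintile's share, its control completion rate and its anticipated intervention rate.

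The target is stated as follows: "To obtain 90% power to detect the interaction as significant at 5% level with 2-sided testing". The answer given is that "in an individually randomised study, we would require 11,714 individuals in each arm". This is divided by 0.8 for practice participation to give 14,643, then multiplied by a variance inflation factor of 2.5, "giving a total study size of 36,608 per arm, a total randomised of 73,216". At 3,000 kits per hub-day that is put at 25 hub-days.

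The size is then raised to 100 hub-days, as protection against failed assumptions and to allow subgroup analyses, and to 150 hub-days (450,000 people) for subgroups by screening round. The subgroup requirement reuses the same base, as 2 x 14,643 per arm, and the 150 hub-days are judged more than sufficient for it. The Data Analyses section sets the matching analysis as a "test of interaction between trial arm and IMD quintile in the LR analysis".

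**The concern.** Detecting a difference between effects takes far more people than detecting an average effect of similar size. Here the effects run only from 1 to 3 percentage points across quintiles, around an average of about 1.9 points. A requirement of 11,714 per arm is of the order one would expect for the average effect, not for the gradient in it.

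The gradient is the primary question, because the primary outcome is uptake in each IMD quintile. If the stated basis is wrong, a null interaction would be read as evidence that the banner leaves the gradient unchanged, from a trial presented as having 90% power at about one-sixth of its planned size (73,216 of 450,000). The protocol's background already reports a null gradient result for the previous GP endorsement trial, so that reading is a real risk.

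**Working it through.** **Inputs (Sample size section and Table 1).** Quintiles are ordered from least to most deprived, with 1:1 allocation.

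| Quintile | Share w | Control p0 | Intervention p1 | Difference | Log odds ratio |
|---|---|---|---|---|---|
| 1 | 0.235 | 0.660 | 0.670 | 0.010 | 0.0449 |
| 2 | 0.235 | 0.626 | 0.641 | 0.015 | 0.0646 |
| 3 | 0.211 | 0.580 | 0.600 | 0.020 | 0.0827 |
| 4 | 0.173 | 0.515 | 0.540 | 0.025 | 0.1003 |
| 5 | 0.146 | 0.426 | 0.456 | 0.030 | 0.1217 |

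**The protocol's chain.** 11,714 / 0.8 = 14,643 (rounded); x 2.5 = 36,608 (rounded); x 2 = 73,216; / 3,000 = 24.4, so 25 hub-days. These steps are correct. Only the starting figure is in doubt.

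**Hand check at 11,714 per arm.** Quintile 5 holds 0.146 x 11,714 = 1,710 people per arm and quintile 1 holds 2,753. The standard error of the risk difference is sqrt{[p0(1-p0) + p1(1-p1)] / (w n)}, which is 1.70 points in quintile 5 and 1.27 in quintile 1. The two effects differ by 3 - 1 = 2 points, with standard error sqrt(1.70² + 1.27²) = 2.12. So z = 0.94. A contrast smaller than its own standard error cannot have 90% power.

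**Trend test using all five quintiles.** Let y be the quintile effect, v its variance for one person per arm, and x = 1 to 5.

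- Logistic: v = 1/[w p0(1-p0)] + 1/[w p1(1-p1)].
- Risk difference: v = [p0(1-p0) + p1(1-p1)]/w.
- With weights 1/v and weighted mean x̄, S = Σ(x - x̄)²/v, and the slope is b = Σ(x - x̄)y/v divided by S.
- n per arm = (1.960 + 1.282)² / (b² S) = 10.507 / (b² S).

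Results:

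- Logistic: b = 0.01889, S = 0.2213, b²S = 7.898 x 10⁻⁵, so n = **133,036** per arm (11.4 times 11,714).
- Risk difference: b = 0.005, S = 3.966, b²S = 9.916 x 10⁻⁵, so n = **105,962** per arm (9.0 times).
- Four-degree-of-freedom heterogeneity test, logistic: n = **194,852** per arm (16.6 times).

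**Power at 11,714 per arm.** 16% (logistic trend), 19% (risk-difference trend) and 10% (four degrees of freedom, logistic). Simulated logistic regression gave 15% for the trend.

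**Attempts to reproduce 11,714.** No genuine interaction test came near it; one-sided testing at 80% power still needs 62,000 to 78,000 per arm. What comes closer does not separate the interaction from the overall effect. The overall comparison of 57.6% with 59.5% needs about 14,430 per arm. An arm-by-quintile slope with no arm main effect needs about 13,000, or 11,564 with equal quintiles.

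**Power at 150 hub-days.** Effective n per arm = 450,000 x 0.8 / 2 / VIF = 180,000 / VIF.

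| VIF | Effective n per arm | Logistic trend | Risk-difference trend |
|---|---|---|---|
| 2.5 (protocol) | 72,000 | 66% | 76% |
| 2.0 | 90,000 | 76% | 85% |
| 1.7 | 105,882 | 82% | 90% |
| 1.5 | 120,000 | 87% | 93% |
| 1.25 | 144,000 | 92% | 97% |
| 1.0 | 180,000 | 97% | 99% |

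The break-even VIF for 90% on the logistic scale is 180,000 / 133,036 = 1.35. If all 450,000 were in endorsing practices, VIF 2.5 would leave 90,000 effective per arm: 76% and 85%. The four-degree-of-freedom logistic test at 72,000 has 45%.

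**Size needed on the protocol's own factors (logistic trend).** 133,036 / 0.8 x 2.5 = about 415,700 per arm, or 831,000 in total; / 3,000 = 277 hub-days.

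**The stated 73,216 at VIF 1.** 73,216 x 0.8 / 2 = 29,286 per arm, giving 33% (logistic).

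**Smallest screening-round subgroup.** 67,500 / 2 / VIF 2 = 16,875 effective per arm, or 13,500 after the 80% participation. Trend power is 21% to 25%, or 18% to 21%.

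**The case against.** The strongest reply is that the trial does not run at 73,216. It runs 150 hub-days, and the protocol enlarged it partly in case its assumptions failed. In addition, every IMD quintile can occur within a hub-day, so a day-level shift in uptake largely cancels from an arm-by-quintile contrast. The inflation factor for that term may therefore be well below 2.5, and at a factor of 1.35 or less the trial has 90% power on the logistic scale. This stands as far as it goes: the trial as run may have adequate power. But the protocol applies 2.5 to this interaction and gives no separate value for it. Even at a factor of 1, the stated 73,216 falls far short.

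A second reply is that the figure came from a published method that is not in the documents. How 11,714 arose is therefore unknown, and the match to an overall-effect calculation is only approximate. The finding does not depend on the cause: any valid method must respect the standard errors that Table 1 implies, and the gap is at least nine-fold.

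Third, the choice between a one- and a four-degree-of-freedom test can be left to a statistical analysis plan. That is fair, and that part of the advice is secondary.

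**Conclusion.** The concern holds. On Table 1's rates, 11,714 per arm gives 10% to 19% power for the interaction, not 90%. The requirement is about 106,000 to 133,000 per arm for a trend test, with the planned logistic analysis at the upper end, and about 195,000 for a four-degree-of-freedom logistic test. All later sample-size figures, including the subgroup requirement, inherit the error.

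For the trial at its fixed 150 hub-days, power on the protocol's own factors is about 66% (logistic trend) or 76% (risk difference). Whether it reaches 90% depends on an inflation factor for the interaction term that the protocol does not give. These results assume Table 1's shares and rates, 1:1 allocation, linear quintile scores and normal approximations. Power for overall uptake is not in question.

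**What to change.** - Recompute the base figure for the interaction coefficient with the arm main effect in the model, and replace 11,714, 14,643, 36,608, 73,216 and 25 hub-days.
- State the interaction power at the fixed 150 hub-days over a range of inflation factors: about 66% at 2.5, 90% at about 1.35 and 97% at 1 for the logistic trend.
- Estimate the inflation factor for the arm-by-IMD term itself from the ASCEND GP endorsement data.
- Correct the subgroup statement. On the protocol's factor of 2, the smallest screening-round subgroup has about 18% to 25% power for the interaction.
- Remove any suggestion that 150 hub-days far exceeds what the gradient question needs.
- As a secondary point, name the primary interaction, in the protocol or the analysis plan, as a one-degree-of-freedom linear trend across quintiles. That matches the posited pattern and avoids the lower power of the four-degree-of-freedom test.

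The cost is a re-run of the power calculation and new wording. No participants are added, and the stated power becomes less favourable.
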